#### 11. PROCEDURES INVOLVED

Patients who are seen at the four UMass Memorial Health OB/MFM clinics in Worcester, MA will be recruited for the study. Participants will be recruited with the use of culturally sensitive recruitment materials and outreach plans vetted by the study's Patient Advisory Group (approved through STUDY00000395). Participants will be identified using a list generated by the Research Informatics core, through direct referrals from OB/MFM providers and community-based organizations via flyers, emails, and social media messages. Flyers (electronic and print) will be shared with community partners (e.g., Together For Kids Coalition, Worcester YMCA) via email or via hard copies. Community partnering organizations and individuals in the patient advisory group may post these flyers on their websites and social media platforms. Invitation letters will also be sent through MyChart (patient portal) and to home addresses 5–7 days before clinic visits with an opt-out link and phone number. Follow-up calls will be made to assess interest from people who do not respond to the invitations within 1-2 days before clinic visits. We aim to enroll 50% Black, Hispanic, and Asian pregnant individuals, as these populations need to be overrepresented to mirror disease presentation and achieve equitable representation.

Participants will be seen during their in-patient encounters or outpatient clinic visits to be consented if interested in the study and after providing more information about the study. After consenting, participants will then be randomized to Moms@Home arm or the ESC arm of the study using a permuted block randomization method stratified by clinic, in blocks of multiples of two. Those not providing consent will be asked a few questions to collect information on why they are declining participation.

A contact list of people declining to participate will be stored in Redcap and destroyed 6 years after study completion.

OB/MFM caregivers will be introduced to the Moms@Home approach and trained on the HBPM report (which will be delivered every 2 weeks during the study) at monthly OB/MFM department meetings and through job aids leading up to and during the start of the study.

#### **Study arms:**

**Moms@Home intervention arm:** Participants randomized to Moms@Home will receive the Moms@Home app ( $\pm$  Samsung smartphone), the digital BP monitor and cuff, and FitBit activity tracker. An orientation, FAQ sheet and HBPM pamphlets will include HBPM instructions, safety protocols, an introduction to the app, and tech support for the digital BP monitor, app, and FitBit. The FAQ sheet and HBPM pamphlet will be generated and submitted through a later modification of the IRB for approval before use. Participants randomized to the Moms@Home intervention arm will be helped by research staff to download and set up the MDH app and will be provided with a Bluetooth enabled blood pressure cuff and a FitBit that syncs with MDH .

## **INVESTIGATOR STUDY PLAN – Moms@Home**

### **V1.0**

Participants in the Moms@Home arm who do not have a smartphone, or have a limited data plan and prefer a study phone will be provided with a study smartphone, which they will return after their time on the study. Participants will each select personalization for daily notifications and set one personal goal. Participants will also be reminded to take daily home blood pressure measurements to be synced into the app.

**Enhanced Standard Care (ESC) arm:** Participants randomized to Enhanced Standard Care (ESC) will receive the digital BP monitor and cuff, a paper diary to record BP values, and a FitBit activity tracker. A modified orientation and FAQ sheet will include the same HBPM instructions, safety protocols, and tech support for the digital BP monitor and FitBit. Participants will each set one personal goal. Participants will also be reminded to take daily home blood pressure measurements to be recorded in the paper diary.

At home, over the 8-week RCT, participants will be instructed to measure their BP daily (2 readings, separated by 1 min) after a 3 min rest period. An HBPM video for reference will be part of the Moms@Home portal. The Moms@Home portal can be programmed with English or Spanish as default language and all videos will have Spanish subtitles. Traffic light (red, yellow, green) alerts and actions for abnormal BP values will be reviewed using a teach-back method. Participants will also be instructed to wear the study FitBit for daily activity and heart rate monitoring. Data from the FitBit will be transmitted through the MDH app to the study team for participants randomized to the intervention arm. For participants who are randomized to the enhanced standard care arm, de-identified physical activity i.e. daily steps, heart rate data and sleep data will be collected via encrypted methods through the FitBit app. Staff will be able to confirm data transmission prior to the participant heading home. The research team will call participants 1–3 days after their scheduled start to address any concerns, ensure data capture, and provide tech support.

Participant data will be collected at baseline (study entry) and the 8-wk follow-up in the privacy of the OB/MFM office (before or after clinic visits). Participants will be asked about their age, ethnicity/race, medication use, baseline HBPM use, and health literacy. If the 8-wk follow-up cannot be scheduled in person, this will be conducted over the phone or over Zoom. All 4-week follow-up visits will be done through a phone check-in. Study staff responsible for outcome assessment will be blinded to group assignments. Assessments will be pre-tested to ensure the time burden does not exceed 30 minutes.

**Post-intervention focus group:** After completing the 8-wk pilot test, three participant focus groups (intervention arm only, N=5/group, 1–1.5-hours) will discuss their experience and barriers/facilitators to engagement with Moms@Home.

Two focus groups with providers (N=5/group for a total of 10 providers, 1-hour) will focus on the home BP report experience, with one group of low utilizers and a second group of high utilizers of the electronic health record HBPM reports. Verbal consent for providers interested in focus group participation will be documented in Redcap.

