### 10. STUDY ENDPOINTS

#### Aim 1:

##### Primary outcome measures:

- Home Blood Pressure Monitoring (HBPM) adherence at 8 weeks
- Feasibility of Moms@Home – assessed through post-intervention focus groups (intervention group only)
- Acceptability of Moms@Home – assessed through the End-user Mobile Application Rating Scale survey administered at 8 weeks, and the post-intervention focus groups (intervention group only)

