##### Secondary outcome measures:

- Engagement with the Moms@Home mobile app will be measured by number of logins, time spent in the app, and storytelling videos watched (4, 8 weeks)
- BP measures - HBPM measures will be gathered from the Moms@Home app and paper BP diaries. Electronic health record review will be used to determine clinic BP values
- Medication adherence – change in medication adherence will be assessed through a brief survey (baseline, 4, 8 weeks)
- Goal attainment scaling - goal attainment will be rated using a 5-point goal attainment scale (baseline, 8 weeks)
- Physical activity - change in physical activity will be tracked by the FitBit (baseline, 4, 8 weeks)
- Moms@Home app sustainability measured with a short sustainability survey (4, 8 weeks)
- Healthcare utilization measures (ex. # of clinic visits, ED visits, admissions) and clinical outcome measures (ex. gestational age at delivery, preeclampsia) (baseline, 4, 8 weeks)
- Self-efficacy measure using the self-efficacy for hypertension questionnaires (baseline, 4, 8 weeks)

Primary safety endpoints

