## INVESTIGATOR STUDY PLAN – Moms@Home

### V1.0

- N/A

Secondary safety endpoints

- N/A

The primary outcome measures will be assessed using the Observed vs Expected number of HBPM readings recorded for participants over the study period. Group comparison will be done between the Moms@Home group vs ESC group.

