**INVESTIGATOR STUDY PLAN – Moms@Home**  
**V1.0**

and flyers (see attached, with QR code to link to Redcap). We will provide these recruitment materials to our community partners (see section 11). They will have the option to post the flyer to social media groups relevant to their communities. Community partners will also post flyers on church and community boards in areas where they know there will be high traffic.

Participants will be screened for eligibility by study staff (see section 6).

Participants who do not opt out and are eligible will be seen during their clinic visits and given further information about the study, as well as potential risks and benefits. If the participant is interested, the consent form will be shared with them and a more detailed conversation regarding the risks and benefits of enrollment will be had. If consent is declined, the participant will be asked a few questions to collect information on why they are declining participation.

To recruit the 10 OB/MFM providers, we will reach out in person or through personal e-mail invitations to individual providers who see patients enrolled in the study. We will also attend department meetings to advertise the opportunity until we reach the target number, aiming for 5 high utilizers and 5 low utilizers (as described in section 11.)

A study stipend will be provided to all participants who complete the baseline (\$25) and 4-week (\$25) assessments. An additional \$75 will be provided to participating subjects upon completion of the 8-week assessments and returning the BP monitor, FitBit, and Samsung phone (if applicable). Both arms of study participants will be eligible for these stipends, totaling \$125. Moms@Home intervention group participants will be compensated \$50 for completing the focus groups, and caregiver participants will be compensated \$100 for completing focus groups.

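### The protocol claims blinded outcome assessment without limit, but this cannot hold for HBPM adherence or for staff who give the app surveys

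*Protocol*

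**What the plan says.** Section 11 (Procedures involved), in the paragraph on data collection, states: "Study staff responsible for outcome assessment will be blinded to group assignments". The sentence is not limited to particular outcomes or staff.

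Section 10 (Study endpoints) and the study-arm descriptions in section 11 specify how the outcomes arise:

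- **HBPM adherence (primary).** It rests on the "Observed vs Expected number of HBPM readings recorded for participants over the study period". On the source of readings, section 10 says "HBPM measures will be gathered from the Moms@Home app and paper BP diaries". Section 11 assigns the two sources by arm. For Moms@Home: "Participants will also be reminded to take daily home blood pressure measurements to be synced into the app". For ESC: "Participants will also be reminded to take daily home blood pressure measurements to be recorded in the paper diary".
- **Acceptability (listed as primary).** This is "assessed through the End-user Mobile Application Rating Scale survey administered at 8 weeks", together with focus groups, and the item is marked as intervention group only.
- **App sustainability (secondary).** The app survey is scheduled at 4 and 8 weeks. ESC women do not receive the app.
- **Self-reported secondary outcomes.** Self-efficacy and medication adherence are collected at baseline, 4 and 8 weeks, and goal attainment at baseline and 8 weeks.

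Section 11 makes every 4-week follow-up a phone check-in. The 8-week follow-up is in the clinic, or by phone or Zoom if that cannot be arranged. Section 23 (Resources available) has research assistants trained both to consent women and to administer surveys, and has data analysts help to input data. It names no separate blinded assessor.

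**The concern.** A statement of blinded assessment tells readers that knowledge of the arm could not colour the measurement. Here the plan's own procedures disclose the arm at two points: when raw HBPM readings are handled, and when app-specific surveys are given.

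Two things are at stake. First, a trial report that repeats the sentence would credit the primary outcome with a protection it does not have. Second, if one member of staff gives both an app survey and the self-report instruments that both arms answer (self-efficacy, medication adherence, goal attainment), those answers may be elicited with the arm known. Section 13 intends the pilot to supply effect sizes and other parameters for a larger trial, so the protection behind those estimates should be described accurately.

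**Working it through.** **1. Does any stated figure depend on blinding?** Section 13 gives 10% versus 35% adherence, a two-sided chi-square test, alpha 0.05, 80% power and 43 per arm. With the pooled-variance formula and mean proportion 0.225:

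n = [1.96 × √(2 × 0.225 × 0.775) + 0.842 × √(0.10 × 0.90 + 0.35 × 0.65)]² / 0.25² = (1.157 + 0.474)² / 0.0625 ≈ 42.6, so 43 per arm.

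Power at 43 per arm is 80.4%. The figure reproduces, and blinding plays no part in it.

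**2. Can the claim be met? Outcome by outcome:**

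| Outcome | How it is obtained | Can the person handling it be blind, as described? |
|---|---|---|
| HBPM adherence | App sync (Moms@Home) or paper diary (ESC) | No at entry or raw count; the medium is the arm. No masked transcription is described |
| App rating, 8 weeks | Survey, intervention group only | No, for whoever gives it |
| App sustainability, 4 and 8 weeks | Survey about the app | No, for whoever gives it |
| Self-efficacy, medication adherence, goal attainment | Arm-neutral self-report | Only if kept apart from the app items; the protocol does not say |
| Clinic BP, utilization, pregnancy outcomes | Record data | Yes in principle, for an abstractor who is not told the arm |

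The first three rows contradict the unlimited sentence. The fourth is undetermined. The last is compatible with it.

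**3. Could the primary outcome be affected?** The documents give no error rate, so what follows is purely an assumption. Suppose there is no true effect, there are 43 per arm, and a share u of non-adherent Moms@Home women is wrongly scored adherent. The apparent rate becomes p + u(1 − p), which is compared with p in ESC by the same two-sided 5% test.

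| True adherence p, both arms | u = 0 | u = 5% | u = 10% | u = 15% |
|---|---|---|---|---|
| 10% | 5% | 10% | 22% | 39% |
| 35% | 5% | 6% | 10% | 15% |

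For example, p = 0.10 and u = 0.10 give 0.10 + 0.10 × 0.90 = 0.19, and the test rejects about 22% of the time. The table shows that the test is sensitive to one-sided scoring error. It does not show that such error will occur. Counting readings leaves limited room for judgement, so u could be close to zero.

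**The case against.** The strongest reply is that silence about role separation is not a statement that there is none. The protocol names a coordinator, research assistants and data analysts. Section 26 has data entered on iPads into REDCap and through the app, so app surveys might never pass through the assessor. Counting readings is fairly objective, and section 13 plans double entry and bias checks. Much of this stands. It limits the likely bias, and it means blinding may hold for some outcomes. It does not rescue a sentence without exceptions, because the arm is still visible to whoever handles the raw readings or gives an app survey.

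A reader might infer more than the documents support, in four ways:

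- *Everyone who assesses outcomes knows the arm, and every Moms@Home woman is identified at both follow-ups.* This assumes that one person gives all instruments, which no section says.
- *Device return unmasks the 8-week visit.* Section 24 ties the last stipend to completing the assessments and "returning the BP monitor, FitBit, and Samsung phone (if applicable"). Only some Moms@Home women hold a study phone, nothing says that the assessor collects it, and the 8-week contact may be remote. It is at most a minor added cue.
- *The bias on the self-report scales can be sized.* At 43 per arm the detectable difference is (1.96 + 0.842) × √(2/43) = 0.60 SD, so an interviewer-induced shift of 0.1 to 0.3 SD would be 17% to 50% of it. The arithmetic is right, but the shift is assumed and the trial is not powered on those scales.
- *Blinding would make the adherence comparison fair.* Automatic sync versus a self-written diary is a difference in measurement. It may matter more, and blinded assessors would not remove it.

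**Conclusion.** The unlimited blinding statement cannot hold as written for HBPM adherence, or for staff who give the app rating or app sustainability survey. This follows from comparing sections 10 and 11 and needs no assumption. Confidence is high for the app-versus-diary conflict. For the arm-neutral self-report instruments, loss of blinding is plausible but depends on who delivers them, which the protocol does not fix. The size of any bias cannot be derived from the document, the sample size is unaffected, and no bias in a particular direction is shown. The defect is a stated design property that the described procedures do not provide. It should be corrected because the correction is cheap and the statement would otherwise carry into the report.

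**What to change.** 1. **Limit the statement in section 11.** Claim blinding only for outcomes that can be assessed blind, for example chart-abstracted clinic BP, utilization and pregnancy outcomes, by an abstractor who is not told the arm. Section 11 mentions HBPM reports in the electronic record, so the abstractor should not open them.
2. **Say that HBPM readings are captured with the arm known.** Diaries still have to be transcribed by someone. After transcription, derive adherence with one fixed, programmed counting rule applied identically to the diary data and the app data.
3. **Order the instruments.** Have women complete self-efficacy, medication adherence and goal attainment before any app-specific item, by self-completion in REDCap where feasible. At the 4-week phone contact, or where language help is needed, staff ask the arm-neutral instruments due at that contact first. Section 30 plans Spanish translation of the surveys only if more than 3 Spanish speakers enrol, so such help should be expected.
4. **Put the app surveys and device return last.**

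The cost is protocol wording, survey order in REDCap and a short counting specification. The reported blinding status becomes less favourable, and some women will need help with self-completion. No additional assessor and no change in sample size is required.

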## **INVESTIGATOR STUDY PLAN – Moms@Home**

### **V1.0**

All focus groups will be held at UMass if in-person (in the ACC building 4th floor conference room or the Memorial campus Peter Levine or 4-West conference room) or on Zoom depending on the schedules/preferences of the participants. These groups will be co-led by [name] and a research coordinator trained in qualitative interviews. Both participant and provider semi-structured guides will be developed using the implementation measures of acceptability, appropriateness, and feasibility. The semi-structured guides will be submitted through a later modification of the IRB application for approval before the interviews are conducted. The focus group recordings will be uploaded to the password protected UMass Chan QMC network drive. Back-up copies of the video files will be stored in an external, password-protected hard drive and a Secure Digital (SD) card. Transcripts will be stored in the same hard drive and a password protected UMass Chan QMC network drive.

#### **12. DATA AND SPECIMEN BANKING**

All participants will be assigned a participant ID. Redcap and the Moms@Home app will be used for data collection and data banking. All digital data will be password protected and encrypted so that only research personnel can access stored data using the RedCap system.

We will create a master list linking the study IDs to identifiers which will be stored in RedCap. Access to this master list will be limited to only members of the study team members that need to work on this list. We will destroy the master list of identifiers 6 years after study completion. We may use the de-identified research data in other future research. We may also share de-identified research data with researchers that are not part of UMass Chan. In these cases, we will not share names or other details that directly identify participants.

Recordings from the focus groups will be destroyed after verification of notes. Detailed field notes, de-identified transcripts and linking documents, and codebooks will be maintained for 6 years after study closure. The study team will ensure the appropriate files are deleted from the external hard drive, QMC drive, and SD card as specified.

According to our study's data management and sharing plan (DMSP), de-identified human subjects' data from the study will be available in clinicaltrials.gov. "The final dataset will include de-identified self-reported demographic and behavioral data from participants and home blood pressure monitoring (HBPM) data from the Moms@Home app. If acceptable to NHLBI, we will work with the NHLBI BioData Catalyst (BDC) to deposit the appropriate data. Otherwise, this final dataset will be kept on hand and distributed upon reasonable request after an appropriate data-use agreement has been put in place. All data will be de-identified prior to release."

#### **13. DATA ANALYSIS AND MANAGEMENT**

##### **Provide a power analysis and/or support for the sample size proposed for this study**

Power calculations for this pilot trial are based on a 2-group, 2-sided Chi-square test of proportions with alpha=0.05. Assuming the intervention will improve HBPM adherence from 10% to 35% (based on our prior work with non-pregnant adults with HTN), we will achieve 80% power when the sample size is 43 per arm (N=86). We will recruit 100 participants to account for ~15% attrition. We base our proposed sample size also on pragmatic considerations related to recruitment, retention, and our focus on feasibility, providing important information for design and recruitment for a future R01 to test Moms@Home in a large RCT.

## **INVESTIGATOR STUDY PLAN – Moms@Home**

### **V1.0**

#### **Describe the data analysis plan, including any statistical procedures**

We will compare HBPM adherence (primary outcome) between the two arms (Moms@Home and ESC). Other outcomes (see section 10) will be compared using generalized estimating equations accounting for the appropriate distribution (e.g., binomial — dichotomous outcome such as HBPM adherence, or Poisson/Negative Binomial — count). We will quantify missing data and dropouts and examine reasons for ineligibility and discontinuation. All data distributions will be examined, and summary statistics calculated by group using an intention-to-treat approach. We will also include other potential modifiers of the intervention effect, potential confounders, and other covariates of interest. In the event of possible effect modification, we will explore the nature of the relationship through the use of interaction terms and subsequent subgroup analysis. This approach will be used for measures with pre-post measurements as well as those collected post-implementation only. Although the pilot study may not have adequate statistical power for testing our hypotheses of improved BP control and medication adherence, we will conduct an exploratory analysis of any treatment effects. We will also examine HBPM adherence by race/ethnicity. Per-protocol analysis will also be performed using all data available from randomized participants without replacement of missing data. Goal attainment scaling, step count, and sleep duration will be characterised for each participant, and then compared between the Moms@Home and ESC groups using a Wilcoxon-Mann-Whitney rank-sum test. In an exploratory analysis, we will compare HBPM, BP control, activity, frequency of visits, and pregnancy outcomes between the primary groups and subgroups (stratified by race/ethnicity, health literacy, income level, age, obesity, and trimester). Qualitative analyses will use applied thematic and content analysis for post-intervention focus groups. All quantitative analyses will be conducted using SAS 9.4 or STATA version 18. We will estimate relevant parameters including estimates of trial retention, intraclass correlation coefficient, standard deviation, and effect size for future R01 power calculations.

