## **22. SETTING**

Subjects will be identified and recruited in the four OB/MFM clinics at UMass Memorial Hospital (mentioned above) from where they are referred and from the UMass Memorial Hospital inpatient service to enroll in the study. Consenting will happen in private rooms at the OB/MFM clinics or in private rooms in the hospital. Subjects will be given adequate time to have all their questions answered and to carefully consider participation. EHR data collection and chart review will be done in the investigators' private offices and in touch-down spaces in the clinic and hospital.

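### Randomisation is stratified by clinic, but the stated primary adherence comparison carries no clinic term; naming one is a small, nearly free improvement

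*Protocol*

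**What the plan says.** - **Design.** Protocol Section 11 allocates women "using a permuted block randomization method stratified by clinic, in blocks of multiples of two". The number of strata is given there, "Patients who are seen at the four UMass Memorial Health OB/MFM clinics in Worcester, MA will be recruited for the study", and again in Section 22, "Subjects will be identified and recruited in the four OB/MFM clinics at UMass Memorial Hospital".
- **Sizing.** Section 13 bases power on a calculation "based on a 2-group, 2-sided Chi-square test of proportions with alpha=0.05". Its rates are "Assuming the intervention will improve HBPM adherence from 10% to 35" per cent, giving 43 per arm (N=86) for 80% power, with 100 women to be recruited.
- **Primary analysis.** Section 13 states: "We will compare HBPM adherence (primary outcome) between the two arms (Moms@Home and ESC"). It names no test, model or clinic term.
- **Nearby text that bears on this.** The next sentence assigns generalized estimating equations to the other outcomes, yet gives HBPM adherence as its example of a binomial outcome. Later comes "We will also include other potential modifiers of the intervention effect, potential confounders, and other covariates of interest". Clinic is not named in either place, and no sentence says that clinic will be left out.

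**The concern.** Permuted blocks within clinic balance the arms inside each clinic, so differences in adherence between clinics largely drop out of the true variability of the treatment difference. An analysis that ignores clinic still counts those differences in its standard error. The standard error is then too large, the test rejects less often than its nominal level under the null, and the confidence interval is wider than it needs to be. The design pays for precision that the analysis does not collect. At stake are a few points of power and a little interval width in a trial of about 100 women whose effect estimate is meant to inform a larger trial.

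**Working it through.** **1. Reproduce the plan's figure.** Inputs from Section 13: control 10%, intervention 35%, two-sided alpha 0.05, power 80%. With pooled variance and no continuity correction,

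n = [1.960·√(2·0.225·0.775) + 0.8416·√(0.10·0.90 + 0.35·0.65)]² / 0.25² = (1.157 + 0.474)² / 0.0625 = 42.6, so 43 per arm.

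The stated figure is right. Formula power is 80.4% at 43 per arm and 86.1% at 50 per arm.

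**2. The two tests compared.**
- Unstratified chi-square: z = (p̂₁ − p̂₀) / √[p̄(1 − p̄)(1/n₁ + 1/n₀)].
- CMH by clinic k: [Σ(x₁ₖ − n₁ₖmₖ/Tₖ)]² / Σ[n₁ₖn₀ₖmₖ(Tₖ − mₖ) / (Tₖ²(Tₖ − 1))], where x₁ₖ is the number adherent in the intervention arm, mₖ the number adherent in both arms and Tₖ the number of women in the clinic. No continuity correction.

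**3. Assumptions.** The protocol gives no clinic sizes or clinic-specific rates. Clinic log-odds are taken as evenly spaced over ±d, the overall rates are held at 10% and 35%, and adherence is treated as binary, as in the sizing. Clinics have 22, 22, 21 and 21 women (N=86), with permuted blocks of 4 and 40,000 simulated trials per row. Type I error is at 22.5% adherence in both arms.

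| Clinic spread (log-odds) | Power, chi-square | Power, CMH | Change (points) | Type I, chi-square | Type I, CMH |
|---|---|---|---|---|---|
| none | 82.4% | 82.0% | -0.4 | 5.2% | 5.1% |
| ±0.25 | 82.5% | 82.2% | -0.4 | 5.0% | 4.9% |
| ±0.5 | 82.7% | 82.9% | +0.2 | 4.9% | 5.0% |
| ±1 (control rates 3–20%) | 83.0% | 84.6% | +1.5 | 4.1% | 4.9% |
| ±1.5 (control rates 2–24%) | 84.2% | 87.7% | +3.4 | 3.4% | 4.9% |

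Changes are taken before rounding.

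**4. Sensitivity.**
- *Exact balance within clinics* (11, 11, 11 and 10 per arm; 100,000 trials), with spread given as a log-odds SD: SD 0, 82.7% vs 81.9% (-0.8); SD 0.5, 83.1% vs 83.3%; SD 1.0, 84.4% vs 86.8% (+2.4); SD 1.5, 85.6% vs 90.5% (+4.9). The last row has control rates from 0.7% to 28.7%, so it is extreme.
- *Unequal clinics* (35, 26, 17 and 8 women): 82.0% vs 81.6% with no spread; 84.0% vs 87.5% at ±1.5.
- *All 100 women* (25 per clinic): 87.7% vs 87.3% with no spread; 89.2% vs 91.9% at ±1.5.

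**5. Interval for the risk difference** (10% vs 35%, N=86), unstratified Wald against Mantel-Haenszel. With no clinic differences both are 33.2 points wide with 94.2% coverage. At ±1.5 the unstratified interval is 33.3 points wide with 96.3% coverage; the stratified one is 31.2 points wide with 95.2% coverage.

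**The case against.** The strongest reply is that this is detail for a statistical analysis plan. The primary sentence fixes no method, so it cannot be said to fix the wrong one. Section 13 also gives HBPM adherence as a binomial example for its estimating equations, and such a model can carry a clinic term; the covariate sentence, "We will also include other potential modifiers of the intervention effect, potential confounders, and other covariates of interest", could cover clinic as well. The gain depends on clinic differences that nothing in the protocol documents, among four clinics of one health system in one city. Much of this stands, and it limits the point to an improvement. What remains is that the protocol answers its own request for statistical procedures, names methods for other outcomes, and leaves its one stated randomisation stratum out of the comparison that matters most.

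Five stronger readings are tempting and are not supported:
- *The plan commits to an unstratified primary analysis.* It does not; it names no test for that comparison.
- *The sample size is wrong because it ignores clinic.* Sizing on a simple chi-square and analysing with strata is normal practice. The figure reproduces, and CMH power stays above 80% at 43 per arm in every setting tried.
- *False positives are inflated.* Ignoring clinic pushes the error rate down. With exactly 43 per arm and 10% adherence in both arms, chi-square gave 5.8% with identical clinics and 4.4% at the widest spread. The excess is a small-sample effect, not a result of ignoring clinic.
- *Clinic's absence from the list "stratified by race/ethnicity, health literacy, income level, age, obesity, and trimester" shows that it was excluded.* That list concerns exploratory subgroups and says nothing about adjusting the primary comparison.
- *Covariates should be kept out of the primary comparison.* Nothing in the protocol requires that.

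**Conclusion.** The point holds as a minor mismatch: allocation is stratified by clinic, and the stated primary comparison is not. Under assumed clinic differences, stratifying changes power by about -1 to +3 points, and by up to about +5 points when clinics differ to an extreme degree. The steadier benefit is calibration: at 22.5% adherence and ±1.5 spread, the chi-square's type I error falls to 3.4% while CMH stays at 4.9%. All of these figures assume a binary outcome and clinic differences that the protocol does not give. Section 10 describes adherence through observed against expected readings without a cut-off; for a continuous ratio the direction of the argument is the same, but these numbers do not carry over.

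**What to change.** Add one sentence to the analysis plan in Section 13: the primary HBPM adherence comparison is stratified by or adjusted for clinic. If adherence is binary, this could be a CMH test with a clinic-stratified risk difference and 95% CI, or the binomial model with a clinic term. If it is analysed as a continuous observed-to-expected ratio, use the equivalent clinic-adjusted model.

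The cost is one sentence and no new data. If clinics do not differ, the loss is 0.4 points of power (82.4% to 82.0%) with blocks of 4, or 0.8 points (82.7% to 81.9%) with exact balance within clinics. The 43 per arm, the target of 100 and the covariate sentence can stay as they are.
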